 The guidelines have been developed in conjunction with the upper extremity surgeons to reflect their current practice. The purpose of the guidelines is to reduce inadvertent variability, particularly when residents and other providers provide the post-operative prescription. Despite the guideline, the surgeon is still encouraged to provide the pain medication prescription he/she feels is most appropriate for the patient.

The Patient Education Study Diary includes a daily pain scale, the QoR-15 on day 2, the selected PROMIS short forms on day 3 and knowledge quiz on day 7. It also contains opportunity to report dressing changes, co-analgesic modalities (ice, elevation, etc), and possible medication side effects. There are daily questions regarding confidence, feeling in control, and satisfaction. The final day also has questions regarding how many times the videos were viewed, the number of contacts with a healthcare provider for pain and wound related issues, and concurrent use of other sedating substances (sleeping pills, alcohol, street drugs, other sedating medications). Patients in the control group (wound care) will also record all pain medications used each day along with any side effects of said medications. Participants in the intervention (pain management) group will record their pain medication use in the additional Recovery Medication Diary provided. The patient will return the diary at the first post-operative visit or by mail.

Patients may be contacted by phone within 7-10 days after the appointment if study materials are not complete. Information regarding the initial narcotic prescription, CPT procedure codes, concurrent NSAID prescription, and type of anaesthetic will be obtained from EPIC by chart review.

The patient will be contacted again by phone and/or mail 1 year after surgery (12-14 months) using the contact information available in EPIC to determine the self-reported prevalence of chronic pain and pain medication use (yes or no answers):

1. Do you have pain on a daily or weekly basis?
2. In the past year, have you taken prescription opioid (or narcotic) pain medication most days or most weeks?
3. In the past year, have any other pain medications (prescription or over the counter) most days or most weeks?

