17. **Objectives:** State the research hypothesis or the question that the research will answer. List the research objectives and expected outcomes. **A primary outcome or objective must be identified.** After the statement of the primary objective, secondary objectives may be listed. Objectives should be simple and specific.

Hypothesis: Patient experience and outcome after outpatient upper extremity orthopedic surgery can be improved by a formalized education program (video and handout) regarding post-operative pain management.

Primary outcome:

1. QoR-15 scores (post-operative day "POD" 2),
  - a. 15-question validated outcome measurement tool used in the setting of outpatient surgery which takes about 2.5 minutes to complete and includes pain as one of its outcome domains

Secondary Outcomes:

2. PROMIS short forms administered on POD 3 – (GI belly pain 5a, GI nausea and vomiting 4a, Pain Intensity 3a, Pain Interference 4a, Sleep Disturbance 4a, Cognitive Function 4a)
3. number of narcotic pills used – 7 days,
4. daily pain level (by 0-10 rating scale) – 7 days,
5. patient-reported satisfaction and feeling of control (4 point rating scale)
6. number of pain-related calls/visits to a healthcare provider
7. use of non-narcotic adjunct pain relief medication and modalities
8. incidence of high risk activities (combining narcotics with muscle relaxants/sedatives/alcohol, etc.; combining prn NSAIDs with regularly dosed prescription NSAIDs, exceeding daily recommended doses)
9. incidence of side effects and adverse events,
10. demonstrated patient knowledge as measured by score on the follow-up quiz, and
11. prevalence of chronic opioid use.

Positive improvements in some or all of these measurements are expected with this patient education intervention. The Quality of Recovery-15 survey is a 15-question validated outcome measurement tool used in the setting of outpatient surgery which takes about 2.5 minutes to complete and includes pain as one of its outcome domains

18. **Study Design:** Give a description of the research design including use of placebo, randomization and an explanation of what is experimental. Include type of study: descriptive, retrospective, cross-sectional, longitudinal, prospective observational, pilot, experimental (controlled or non-controlled) or pilot.

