Participants in both arms will complete a Patient Education Study Diary daily for 7 days following their surgery. Patients in the control group (wound care) will also record all pain medications used each day along with any side effects of the medications. Participants in the intervention (pain management) group will record their pain medication use in the additional Recovery Medication Diary provided.

Patients will receive a phone call from either an investigator or the study coordinator on Day 1-3 and Day 5-7 to remind them to complete their diaries and to answer any questions the patient may have (see attached script).

Patients will return their diaries at their first post-operative visit. If they do not bring the diaries to the post-operative visit, they will be given a self-addressed, stamped envelope to facilitate return. Patients will be contacted by phone (with permission) <10 days and 14-21 days following surgery and again 21-28 days after surgery if they have not returned their study materials as a reminder.

The Follow-up Questionnaire will be completed at the 1st post-operative visit, or by phone within 7-10 days of that appointment. The patient will be contacted again by phone and/or mail 1 year after surgery

(12-14 months) using the contact information available in EPIC to determine the self-reported prevalence of chronic pain and pain medication use:

1. Do you have pain on a daily or weekly basis?
2. In the past year, have you taken prescription opioid (or narcotic) pain medication most days or most weeks?
3. In the past year, have you used pain medications (prescription or over the counter) most days or most weeks? (list medications used on a daily or weekly basis for pain)

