## 7. Data Storage, Data Entry and Statistical Analysis

Paper copies of study materials containing confidential patient information will be stored in locked boxes in the nursing station and in locked drawers in locked areas of the clinic/physician offices. Electronic copies of study materials/collection tools containing patient identifiers/confidential information will be stored on the Carilion S drive or on REDCAP as appropriate. All paper and electronic copies will be retained for 7 years and destroyed according to Carilion accepted research procedure.

A working binder will be maintained for logistical purposes to track and coordinate enrollment, follow-up phone calls and visits, and collection of study materials. The binder will list subject number, name, phone number, dates of surgery and visits, and have columns to track progress through the study protocol. It will be maintained in a locked drawer in a locked office.

Data Entry will be carried out by the investigators.

Statistical analysis will be carried out with assistance of a Carilion Clinic biostatistician. Statistical analysis will include description of the study population and comparison of study groups based on demographic variables. This will include age, surgical site (hand, wrist, forearm/elbow, humerus/shoulder), and type of anesthesia (general vs. local) as these have been shown to affect post-operative narcotic use. Analysis regarding the effect of age, gender, and surgery and medication related variables on the outcome measures will also be carried out. Primary and secondary outcome measures will be

- a. QoR-15 scores (primary outcome),
- b. PROMIS scores,
- c. number of narcotic pills used,
- d. daily pain level (by 0-10 rating scale),

- e. patient-reported satisfaction and feeling of control (4 point rating scale),
- f. number of pain-related calls/visits to a healthcare provider
- g. use of non-narcotic adjunct pain relief medications and modalities,
- h. incidence of high risk activities (combining narcotics with muscle relaxants/sedatives/alcohol, etc.; combining prn NSAIDs with regularly dosed prescription NSAIDs, exceeding daily recommended doses)
- i. incidence of side effects and adverse events,
- j. demonstrated patient knowledge as measured by score on the follow-up quiz, and
- k. prevalence of chronic pain, long term narcotic and non-narcotic pain medication use. .

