**Power Calculation and Sample Size:**

The QoR-15 score is a validated outcome metric for quality of recovery (Stark 2013) and is the primary outcome measure for this study. Thus, the QoR was chosen for the power analysis and sample size calculation. Using data from Stark et al 2013, the expected values for the QoR score are average ( $\mu$ ) of 120 and standard deviation ( $\sigma$ ) of 25. We would consider a difference of 8 points to be

clinically significant. Thus, using these values and with an  $\alpha$  of 0.05 and  $\beta$  of 0.8, the calculated sample size is  $n = 154$ . Our study design will allow for a maximum attrition of up to 20% (39 patients), thus we will enroll 200 patients per group (rounding up from 193).

Our group performs approximately 2000 procedures annually (1,973 in FY2016), of which we anticipate 80% will be eligible for this study. Assuming a 50% enrollment rate, it is reasonable to project completion of enrollment in 6 months. Notably, the enrollment rate amongst eligible patients for our completed study on narcotic use after minor hand surgery was greater than 95%. However, this study does require more patient engagement, and so a more conservative estimate has been used. The video length as well as the length and complexity of the diary and surveys are being minimized. Patients will be contacted by phone (with permission) as well as have contact at their follow-up appointment(s) to assist with completion and return of materials. Self-addressed stamped return envelopes will be provided when the patient fails to bring study materials to the first post-operative visit.

Statistical review was conducted by: [name] (name of statistician)  
Carilion (Department/Institution of statistician)

If no statistical review was done, explain why:

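### The 1-year pain question is collected as one yes/no answer that merges daily with weekly pain, and no pain with less-than-weekly pain; graded answers would keep that information at almost no cost

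*Protocol*

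**What the plan says.** Section III, item 15 (Study Abstract) describes a phone or mail contact 12 to 14 months after surgery "to determine the self-reported prevalence of chronic pain and pain medication use (yes or no answers". Of its three questions, only the first concerns pain: "Do you have pain on a daily or weekly basis".

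Item 20 (Methodology, step 6, Data Collection) repeats that question with the same wording and no finer frequency scale. The one detail it adds belongs to the third question, on medication: "list medications used on a daily or weekly basis for pain". That records drugs, not how often the patient has pain.

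Item 20, step 7, lists as its last outcome "prevalence of chronic pain, long term narcotic and non-narcotic pain medication use". The measured-outcomes paragraph of item 15 and the outcome list in item 21 carry the same outcome. Item 17 (Objectives) names only "prevalence of chronic opioid use" for the long term and does not mention chronic pain.

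Power is addressed in item 22 for the primary outcome alone: "Thus, the QoR was chosen for the power analysis and sample size calculation".

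**The concern.** How often a patient has pain is a graded quantity: none, less than weekly, weekly, daily. The protocol cuts it once, between less than weekly and weekly, and does so when the answer is collected. Two kinds of change then disappear: a patient who moves from daily to weekly pain, and one who moves from occasional pain to none. Only a move across the cut is counted.

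An analysis plan could not repair this, because the detail is never recorded. Elsewhere the trial grades pain (a daily 0-10 rating, PROMIS Pain Intensity 3a and Pain Interference 4a), and the protocol gives no reason for a single cut at 1 year. At stake is how much a long-term comparison of pain can show, and how a null result on it should be read.

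**Working it through.** **1. The plan's own figure.** Item 22 gives mean 120, SD 25, a difference of 8, alpha 0.05 and 0.8 (written as beta, functioning as power). Per group, n = 2(1.960 + 0.842)² × 25² / 8² = 153.3, so 154. Allowing 20% attrition, 154/0.8 = 192.5, so 193, rounded to 200. The figure reproduces with two-sided alpha. It concerns QoR-15 and says nothing about the 1-year item.

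**2. Assumptions needed for the 1-year item.** The protocol states no prevalence, category split or effect. I assume:
- a normal latent pain-frequency scale with a shift of 8/25 = 0.32, borrowed from QoR-15 on day 2;
- 154 per arm and two-sided alpha 0.05;
- several control splits, written none / less than weekly / weekly / daily.

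**3. Formulas, for the split 50/20/15/15.**
- *Shift.* Control cumulative proportions are 0.50, 0.70 and 0.85, with thresholds 0, 0.524 and 1.036. Adding 0.32 and converting back gives 0.626, 0.801 and 0.913. The intervention arm is therefore 62.6/17.5/11.2/8.7, and daily-or-weekly pain falls from 30.0% to 19.9%.
- *Yes/no comparison.* Power = Φ(|p1 − p2| / √[(p1(1 − p1) + p2(1 − p2))/n] − 1.96) = Φ(0.1008/0.0490 − 1.96) = 53.9%.
- *Four levels.* This is a Wilcoxon test with ties. Each category is scored at its mid-rank in the pooled distribution. The difference in mean score is about 0.071 and its null standard error about 0.0297, so power is about Φ(2.40 − 1.96) = 67%. A different variance estimate gives 67.9%, so results are good to about 1 point.

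**4. Four control splits, each with 20% less-than-weekly pain.**

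| Control split (%) | Daily or weekly, control → intervention | Yes/no power | Daily/weekly separated only | All four levels | Total gain |
|---|---|---|---|---|---|
| 60/20/10/10 | 20.0 → 12.3 | 45.8 | 46.4 | 62.3 | 16.5 |
| 50/20/15/15 | 30.0 → 19.9 | 53.9 | 55.4 | 67.0 | 13.1 |
| 40/20/20/20 | 40.0 → 28.3 | 58.6 | 61.6 | 70.2 | 11.6 |
| 30/20/25/25 | 50.0 → 37.4 | 61.0 | 65.8 | 72.3 | 11.3 |

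Separating daily from weekly alone adds 0.6, 1.5, 3.0 and 4.8 points. At 30% prevalence, separating none from less than weekly alone gives 65.3%, which is 11.4 of the 13.1 points.

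**5. Sensitivity.**
- *Size of the less-than-weekly group, shift 0.32.* At 5% of controls the gain is about 6 points (5 to 7 for prevalence 20 to 50%). At 1% it is about 2 points for prevalence 20 to 30%. At 50% prevalence it stays near 5, nearly all from the daily/weekly split.
- *Shift of 0.2.* The gain is roughly 3 to 8 points when 5 to 20% of controls have less-than-weekly pain.
- *Another model for the daily/weekly split.* Under proportional odds (odds ratio 0.4 to 0.8, daily share of pain 20 to 80%), three levels gain 0.2 to 0.8 points at 30% prevalence and 0.4 to 3.4 at 50%.

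**6. A shift within the merged group.** If 20% daily and 20% weekly become 10% and 30%, the yes/no item reads 40% in both arms and shows nothing. A three-level rank test has only about 10% power here, so the graded answer makes the change visible without making the test strong. If they become 10% and 25%, power is 14.6% for yes/no and 29.1% for three levels.

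**The case against.** The outcome is a prevalence, and a yes/no item is a legitimate way to measure one. Patients with pain rarer than weekly are not cases under the protocol's own question. Most of the extra power therefore belongs to a different comparison, of the whole frequency distribution. On the prevalence itself the change gains nothing. That stands.

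The contact is a brief three-question screen, and item 22 says the length and complexity of the diary and surveys are being kept down. Graded pain is already measured in the first week, when the main hypothesis is tested. The outcome is unpowered, and the Objectives list does not name chronic pain. All of this limits the weight of the point. It does not restore the lost detail, and one item with four answers is hardly longer than one with two.

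A reader might infer that pooling daily with weekly pain costs some 9 to 17 points of power. The documents do not support that. They contain none of the inputs. Gains of that size need an assumed effect borrowed from a different outcome a year earlier and a sizeable group with occasional pain, and they come mainly from the other merge. A reader might also infer that the item cannot detect any change in pain frequency. It can detect any net move across the daily-or-weekly cut.

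**Conclusion.** The point holds as a measurement limitation. A single yes/no answer merges two pairs of distinguishable states, and shifts within either pair are lost at collection. No stated figure is wrong, and the item delivers the prevalence the protocol promises.

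The size of the loss cannot be fixed from the documents. On the assumptions shown, an ordinal comparison with 154 per arm gains between about 2 and 17 points of power. The result depends mainly on the share of controls with less-than-weekly pain and on the assumed shift. The daily/weekly merge accounts for about 1 to 5 of those points. Because the outcome is non-primary and unpowered, this is a cheap improvement and not a flaw in the trial's main conclusion.

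**What to change.** In items 15 and 20, replace the response to the first 1-year question with four categories: none, less than weekly, weekly but not daily, daily. Keep the proportion with weekly or daily pain as the stated outcome; the same answers give it directly. Add an ordinal comparison of the arms as a supportive analysis, using a proportional-odds model or a Wilcoxon test stratified as the randomization is. If a power figure is quoted for it, state the assumed split and shift and show a range.

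The cost is a change of response options in the phone/mail script and the database field, a small IRB amendment, a few more seconds per contact, and a second effect measure to report beside the prevalence difference. No further contact or patients are needed.

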Measured outcomes will include: QoR-15 and PROMIS scores, number of narcotic pills used in the first week after surgery, daily pain level (by 0-10 rating scale), patient-reported satisfaction and feeling of control, related calls/visits to a health care providers, use of non-narcotic adjunct pain relief modalities, incidence of side effects and adverse events, demonstrated patient knowledge as measured by score on the follow-up quiz, and prevalence of chronic pain, long term narcotic and non-narcotic pain medication use. Positive improvements in some or all of these measurements are expected with this patient education intervention.

16. **Background:** Summarize background information about the research question(s.) Tell why the research is needed and include the relevance of this research to the contribution of this field of study. Also, provide references to relevant articles in the literature. (If you have more than 10 references, please submit the list of references as a separate attachment. Otherwise, please insert them here.)

Pain after surgery is a common experience and is not always well controlled. Results from a recent five-year survey of adult surgical patients (N = 300) showed ~86% experienced pain after surgery; of these, 75% had moderate/extreme pain during the immediate post-surgical period, with 74% still experiencing these levels of pain after discharge. Post-surgical pain was the most prominent pre-surgical patient concern, and nearly half reported they had high/very high anxiety levels about pain before surgery.

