#### Exclusion criteria will include:

1. Patients unable or unwilling to provide informed consent
2. Patients unable to unwilling to participate in the trial (poor English language skills, blindness, cognitively disadvantaged, poor literacy skills, other barriers to participation)
3. Patients who are or suspect they may be pregnant.
4. Patients for whom the medical provider, in his professional judgment, does not feel that the study protocol would be appropriate. (to be tracked)

Inclusion and exclusion criteria were selected by the PI with the intention to make the study population as inclusive as possible to represent since the goal of the videos is to have them available

for general patient viewing. Pediatric patients and pregnant patients are excluded as these represent populations with special ethical and medical considerations (such as drug dosing, medication effect on the fetus) which are not addressed in this study. Also, the educational program is designed for adult learners.

20. **Methodology:** List all activities or procedures that will be performed (pre-treatment tests and medications, tests and medications used during therapy, diagnostic tests, x-rays, lab tests, questionnaires and other forms, interviews, chart reviews etc.) Describe how, when and where research activities will be administered and analyzed. **Distinguish any standard processes from those that are research.** Please describe activities/procedures in a step-by-step chronological order. State the length of time subjects will be in the study and the expected amount of time required for each study visit or activity.

1. Recruitment – 10 minutes

A desk-top sign advertising the study will be displayed in patient rooms used by the Hand Section providers for patient visits.

All patients who are consented or scheduled for surgery during a clinic visit with a Hand Section provider at the ION building (when a designated enrollment investigator is present/available) will be considered for the study. These patients will be referred to the designated enrollment investigator, who will present the participation opportunity to the patient after the conclusion of the visit with the provider. The designated enrollment investigator may be a study coordinator, medical student, or other investigator, but will not be the treating physician. Study coordinators will be utilized in this role whenever possible, although scheduling and budget restraints will make mixed coverage necessary.

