    - a. A series of two 6-minute videos. The first video, Managing Pain after Outpatient Surgery, Part 1, discusses a tiered approach to pain management, including rest, ice, elevation, distraction, and medication. Three classes of pain medication commonly used after surgery, including nonsteroidal anti-inflammatories, acetaminophen, and opioids, are discussed, including the role of each medication and the risks and side effects. Naloxone, an antidote to opioid medication for emergency use, is introduced. The second video, Managing Pain after Outpatient Orthopedic Surgery, Part 2, instructs the patient on how to make a Pain Plan with regard to post-operative pain medication, including the use of over the counter pain medications and a medication diary. (12 minutes)
    - b. Recovery Medication Diary (1-7 minutes, daily, for 7 days)
  - 2) Wound Care Education (Control)
    - a. A single video, Caring for Your Closed Wound, discusses the types of sutures that are used to close surgical wounds, the specifics of wound care and dressing changes, swelling management, restriction of physical activity, scarring of the surgical site and

methods to reduce scarring, and guidance on when to call their physician if they suspect something to be wrong following their procedure. (6 minutes)

Patients are encouraged to view the video(s) in the examining room of the clinic before departure on a tablet device. Patients who elect to watch the video will be offered a small bottle of water, due to the extended visit and as a “fidget” to aid in attention. The videos will also be “assigned” to the patient in MyChart through the GetWellNetwork, and also available for viewing online on the Carilion channel on YouTube.

5. Patient packet dissemination (< 1 minute)

All patients in the study will receive an enrollment package with includes a copy of the consent form, video web address, and Patient Education Diary (experimental or placebo version). Patients in the Pain Control Video group will also receive a Recovery Diary corresponding to the video.

6. Data Collection (1-7 minutes daily for 7 days)

Patients are invited to view the video on the GetWellNetwork through MyChart and on YouTube. Viewing will be tracked by patient report, and by tracking views on the GetWellNetwork. (Viewing by patient report will be used in statistical analysis, comparison to GetWellNetwork data will be exploratory.)

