**Patient Demographic Data:**

Name

EMPI

CSN

MRN

Contact phone number

Age

Gender

Pre-existing pain medication use (opioids, acetaminophen, NSAIDS, Lyrica, Neurontin)

Patient race, ethnicity, education level

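### The stated between-arm analysis of the 7-day narcotic count leaves out pre-operative opioid use, so standing regimens add avoidable variance to secondary outcome 3

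*Protocol*

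**What the plan says.** All references are to the Protocol, Section III.

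- **Outcome.** The abstract (item 15) lists the "number of narcotic pills used in the first week after surgery"; the objectives (item 17, outcome 3) list the "number of narcotic pills used – 7 days". Neither limits the count to the post-operative prescription.
- **Data source.** Item 20, step 6: control patients "will also record all pain medications used each day along with any side effects of the medications". For the other arm: "Participants in the intervention (pain management) group will record their pain medication use in the additional Recovery Medication Diary provided". No split between a regular supply and the new prescription is described.
- **Eligibility.** None of the four exclusion criteria in item 19 concerns opioid use. The criteria were chosen "with the intention to make the study population as inclusive as possible".
- **Baseline data.** Item 21 lists "Pre-existing pain medication use (opioids, acetaminophen, NSAIDS, Lyrica, Neurontin") among the data to be collected.
- **Analysis.** Item 22 puts all data into a mixed model ANOVA with post-hoc comparisons by group and names no covariate. Item 20, step 7 adds an analysis of how age, gender, and surgery and medication variables affect the outcomes; pre-operative opioid use is not named.
- **Randomization.** The abstract stratifies by prescription size and by baseline pain medication use. Item 20, step 2 stratifies by six classes of anticipated prescription, and the list of further factors that follows has no entry in the text available.

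**The concern.** A patient on a standing opioid regimen contributes those pills to the 7-day count in either arm. Randomization balances such patients in expectation, so the difference between arms stays unbiased. The spread of the outcome grows, however, and in a mixed ANOVA the arm effect is judged against between-patient variation, which is exactly what grows. The video "instructs the patient on how to make a Pain Plan with regard to post-operative pain medication", so its effect is most plausibly on pills taken for the surgery. A real effect of that kind would be measured with more noise than necessary, although the variable that explains much of the noise is already on the enrolment list. At stake is the power and interval width for one of ten secondary outcomes.

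**Working it through.** **1. The plan's own figure.** Item 22 sizes the trial on QoR-15 with a difference of 8, SD 25, alpha 0.05 and 80% power. Two-sided: n = 2 × (1.96 + 0.84)² × 25² / 8², which gives 154 per group, as stated. Allowing for 20% attrition, 154 / 0.80 = 192.5, so 193, rounded by the plan to 200. This reproduces and is not affected by the present point. No SD, effect or sample size is given for the pill count.

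**2. Model for the pill count (all inputs assumed).** Let total pills = post-operative pills (SD s) + regimen pills, where the latter occur only in a share f of patients, with mean r and SD t, independent of the former. Then:

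- unadjusted variance = s² + f·t² + f(1−f)·r²
- variance after adjusting for user status (yes/no) = s² + f·t²

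Adjustment removes the term f(1−f)·r², the gap between users and non-users. Adding the usual daily number could also remove part of f·t².

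**3. Illustration: s = 8, r = 28 (4 a day), t = 14.** Completers per arm: 200 × 0.80 = 160. Detectable difference at 80% power = 2.80 × SD × √(2/160).

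| Case | Variance | SD | Factor | Detectable difference (pills) |
|---|---|---|---|---|
| No prior users | 64 | 8.0 | 1 | 2.5 |
| f = 5%, unadjusted | 64 + 9.8 + 37.2 = 111.0 | 10.5 | 1.7 | 3.3 |
| f = 5%, adjusted | 64 + 9.8 = 73.8 | 8.6 | 1.15 | 2.7 |
| f = 10%, unadjusted | 64 + 19.6 + 70.6 = 154.2 | 12.4 | 2.4 | 3.9 |
| f = 10%, adjusted | 64 + 19.6 = 83.6 | 9.1 | 1.31 | 2.9 |

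**4. Wider range.** Take s = 8 or 10, f = 5% to 20%, and (r, t) = (14, 7), (21, 10) or (28, 14). For an effect of 0.32 × s at 160 per arm, power without any regimen pills is 0.82.

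- Unadjusted: variance factor 1.12 to 3.57, power 0.77 down to 0.33.
- Adjusted for user status: variance factor 1.02 to 1.61, power 0.81 down to 0.62.
- A middle case (s = 10, f = 10%, r = 21, t = 10): unadjusted variance 100 + 10 + 39.7 = 149.7, factor 1.50, power 0.65; adjusted variance 110, factor 1.10, power 0.78.

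**5. What the plan already does.** Stratifying on baseline medication use, if carried out, would balance users between arms. It yields a smaller standard error only if the analysis also conditions on the strata, and item 22 does not say that it does.

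**The case against.** The strongest reply is that the plan is not blind to baseline use. The abstract stratifies on it, and item 20 promises an analysis of medication variables on the outcomes, among which the pill count is listed. A reader might infer from item 22 alone that baseline use is ignored altogether; that goes too far. What stands against the reply is that the item 20 wording is generic and is not tied to the comparison of arms, and that the abstract and the randomization step disagree on the stratification factors.

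Second, covariates are often left to a statistical analysis plan, which is not at hand. If that plan names pre-operative opioid use in the model for this outcome, the point is met. As written, item 22 states a between-arm analysis without it.

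Third, a reader might conclude that the outcome itself is wrong and should count only pills from the post-operative prescription. The documents do not support that. Reducing narcotic use is a stated premise in the abstract and is not restricted by source. A restricted count would miss surgical pain treated from an existing supply. It would also ask patients to attribute each pill to a supply in diaries that differ between arms, which could misclassify differently by arm and replace noise with bias.

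Fourth, every input to the pill-count arithmetic is assumed, including independence of regular and post-operative use. If regular pills replace prescription pills, the inflation is smaller. This objection stands in full as to size. Nor can it be said that a few regular users dominate the variance: in the illustration they contribute 47 of 111 (42%) at 5% and 90 of 154 (58%) at 10%.

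**Conclusion.** The point holds as an avoidable loss of precision in one secondary outcome. The count is unrestricted, opioid users are eligible, their use is recorded, and the stated comparison of arms does not use it. The direction is secure as long as regimen use adds to the between-patient spread; the size is not known from the documents. Under the illustrative inputs the variance factor is 1.7 or 2.4 unadjusted and about 1.15 or 1.31 once user status is in the model, so adjustment recovers most of the loss without changing the outcome. A reader might infer a bias between arms, or a threat to the primary result. Neither follows: randomization balances prior users in expectation, and QoR-15 and its sample size are untouched.

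**What to change.** Name pre-operative opioid use (yes/no, and usual daily number if recorded) as a covariate in the between-arm model for outcome 3, together with the factors actually used to stratify. Keep total narcotic pills as the outcome. Bring the abstract and item 20, step 2 into line on whether baseline pain medication use is a stratification factor. As a sensitivity analysis, report either the count limited to the post-operative prescription, where the diaries allow it, or the comparison in patients not using opioids before surgery.

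Cost: one covariate and possibly one enrolment field for the usual daily number, since the Protocol does not say that this number is collected. The prescription-only analysis would in addition need the supply to be identifiable in both diaries, and should be read with the misclassification risk in mind.
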